- Proportion of patients with disease resolution on Day 14. Disease resolution is defined as patients who are alive and have a score of 6, 7, or 8 on the NIAID 8-point ordinal scale.
- All-cause mortality rate at Day 14 and Day 60
- Change of clinical status related to COVID-19 on Day 14 compared with baseline according to the NIAID 8-point ordinal scale as listed above
- Proportion of patients requiring invasive ventilation (mechanical ventilator and/or ECMO), or who are not alive on Day 14 or Day 28
- Proportion of patients in each category of the NIAID 8-point ordinal scale
- Time to (first) improvement of at least 1 category on the NIAID 8-point ordinal scale (until Day 28). Patients who did not improve at least 1 category on the NIAID scale or die before Day 28 will be censored at Day 28.
- The odds ratio between MP1032 and SoC and placebo and SoC for the number of patients with clinical status improvement from baseline on the NIAID 8-point ordinal scale (ie, an improvement of at least 1 category) at Day 14 and Day 28
- Total duration of hospitalization on Day 28 and Day 60 (from baseline to discharge; with death censored on the last day of the observed period at Day 28 or Day 60, respectively)

This document is confidential.

Page 32 of 85

MetrioPharm AG	MP1032-CT05	
MP1032	Final	
MetrioPharm AG	MP1032-CT05	
MP1032	Protocol v2.0	

- Proportion of patients alive and testing negative for COVID-19 on Day 14, Day 28, and Day 60
- Safety and tolerability assessed by:
 - Cumulative incidence of TEAEs (summarized by seriousness, severity, relationship to the study medication, outcome, and duration)
 - Vital sign parameters
 - Clinical laboratory parameters
 - Physical examination findings
- MP1032 plasma concentrations and PK parameters (if possible) including maximum observed plasma concentration, area under the concentration-time curve, elimination parameters, apparent body clearance, apparent volume of distribution, trough concentration, average observed plasma concentration at steady state, and other relevant PK parameters assessed via MP1032 plasma exposure on Day 1 and Day 7 in a PK subset of patients

Exploratory endpoints of this study are:

- Change in saturation of oxygen (SpO₂)/fraction of inspired oxygen (FiO₂) ratio (for patients alive) on Day 14 or Day 28 compared with baseline
- Total number of days in the intensive care unit (ICU)
- Duration of invasive mechanical ventilation
- Duration of ECMO

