7.3 End of Study

A patient will have fulfilled the requirements for study completion if/when the patient has completed all study periods, including Day 60 as indicated in the Schedule of Assessments (Table 1).

The end of the study will be the last patient's last visit (ie, Day 60) as indicated in the Schedule of Assessments (Table 1).

SELECTION OF STUDY POPULATION 8

Section 7.1 provides information regarding number of patients planned to be randomized.

81 **Inclusion** Criteria

Individuals must meet all of the following criteria to be included in the study:

- 1. The patient must be willing and able to give informed consent to participate in the study and to adhere to the procedures stated in the protocol or, for adults incapable of consenting due to their medical condition (eg, too weak or debilitated, severe shortness of breath) or due to literacy issues, the patient's legally authorized representative (LAR) must be willing and able to give informed consent on behalf of the patient to participate in the study as permitted by local regulatory authorities, institutional review boards (IRBs)/independent ethics committees (IECs), or local laws.
- 2. The patient is male or female adult aged ≥ 18 years (as per local laws) at the time of giving informed consent.
- 3. The patient is admitted to a hospital and has a positive SARS-CoV-2 test by standard RT-PCR assay or equivalent test. Please note: If the patient has a previous confirmation of SARS-CoV-2 (within 7 days of Day 1), the SARS-CoV-2 test at screening is not required.

This document is confidential.

Page 37 of 85

- 4. The patient has the presence of any symptom(s) suggestive of moderate or severe systemic illness with COVID-19 on Day 1, such as presence of fever (≥38.0°C [≥100.4°F] by any route), loss of smell or taste, cough, sore throat, malaise, headache, muscle pain, gastrointestinal symptoms, shortness of breath upon exertion and/or at rest, or respiratory distress.
- 5. The patient has the presence of moderate to severe clinical signs indicative of moderate or severe illness with COVID-19 on Day 1:
 - a. Moderate:

MP1032

- Clinical signs suggestive of moderate illness with COVID-19, such as respiratory rate ≥20 breaths per minute, SpO₂ >93% (on room air at sea level, if possible), heart rate ≥90 beats per minute
- ii. No clinical signs indicative of severe or critical COVID-19
- b. Severe:

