This document is confidential.

Page 50 of 85

MetrioPharm AG	MP1032-CT05
MP1032	Protocol v2.0

- c. The patient must give informed consent to participate in the study or, for adults incapable of consenting due to their medical condition (eg, too weak or debilitated, severe shortness of breath) or due to literacy issues, the patient's LAR must be willing give informed consent on behalf of the patient to participate in the study as permitted by local regulatory authorities, IRBs/IECs, or local laws.
- d. At the screening visit, the local laboratory may perform COVID-19 testing by standard RT-PCR assay or equivalent test. At screening, a positive test must be available in order for the patient to be randomized on Day 1. If the patient has a previous confirmation of SARS-CoV-2 (within 7 days of Day 1), the SARS-CoV-2 test at screening is not required. On Day 1, Day 14, Day 28, and Day 60, samples will be sent to the central laboratory for COVID-19 testing by standard RT-PCR assay. The result of the COVID-19 tests (positive/negative) must be documented in the eCRF. Further details will be described in the laboratory manual. Please note: If COVID-19 tests are performed at unscheduled time points (eg, according to SoC), findings (ie, positive/negative result) must be recorded in the eCRF.

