The HRQoL will be assessed via the EQ-5D-5L questionnaire (Appendix 2). The EQ-5D-5L is a standardized questionnaire developed by the EuroQol Group as a measure of HRQoL that consists of a descriptive system and a VAS. The descriptive system consists of 5 dimensions: mobility, self-care, usual activities, pain/discomfort, and anxiety/depression. The VAS records the patient's self-rated health on a vertical VAS. This can be used as a quantitative measure of health outcome that reflects the patient's own judgment. The patient is asked to indicate his/her current health state (ie, describe their health "today"). The scores on these 5 dimensions can be presented as a health profile or can be converted to a single summary index number that describes the patient's current health state. The EQ-5D-5L questionnaire has been validated in a diverse patient population in 6 countries and is available in multiple languages. The EQ-5D-5L questionnaire is suitable for completion by adults (EuroQol Research Foundation 2020).

The results of the EQ-5D-5L questionnaire will be recorded at the visits specified in the Schedule of Assessments (Table 1). Please note: This assessment will only be performed in patients who have been discharged from the hospital before Day 60.

15 COVID-19 Testing

Samples for COVID-19 testing will be obtained at the visits specified in the Schedule of Assessments (Table 1). At the screening visit, the local laboratory may perform COVID-19 testing by standard RT-PCR assay or equivalent test. At screening, a positive test must be available in order for the patient to be randomized on Day 1. If the patient has a previous confirmation of SARS-CoV-2 (within 7 days of Day 1), the SARS-CoV-2 test at screening is not required. The result of the COVID-19 tests (positive/negative) must be documented in the eCRF

On Day 1, Day 14, Day 28, and Day 60, samples will be sent to the central laboratory for COVID-19 testing by standard RT-PCR assay. The result of the COVID-19 tests (positive/negative) must be documented in the eCRF. Further details will be described in the laboratory manual.

Please note: If COVID-19 tests are performed at unscheduled time points (eg, according to SoC), findings (ie, positive/negative result) must be recorded in the eCRF.

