15.2 Analysis Sets

Screened Set

The Screened Set will include all patients who give informed consent and are screened. For this group, patient disposition, and reasons for premature study termination or screening failure will be described.

Randomized Set

The Randomized Set will include all patients randomized. Unless specified otherwise, this set will be used for all subject listings with exception of the listing presenting screening failures and the respective reason(s) for screen failure.

Intention-To-Treat Set

The Intention-to-Treat (ITT) set, correspond with randomized set, will include all randomized patients irrespective of any deviation from the protocol or premature discontinuation from study drug/withdrawal from study. The treatment group assignment will be designated according to initial randomization. The ITT will serve as the basis for the analysis of efficacy and summary of demographics and baseline characteristics.

Per Protocol Set

The Per Protocol Set (PPS) will include all patients from ITT who received at least 1 dose of study drug and who do not have any major protocol deviations impacting the efficacy assessments. The PPS will be used for supportive analyses of efficacy.

Safety Set

The Safety Set (SS) will include all randomized patients who receive at least 1 dose of study drug. The treatment group assignment in the SS will be defined by the treatment actually received. The SS will be used for the analysis of safety.

PK Analysis Set

The PK Analysis Set (PKS) will include all the patients who have been administered active study drug and have at least 1 postdose evaluable plasma concentration after Day 1 dose.

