A similar analysis of covariance approach as described above for Day 28 will be applied for the analysis of the change of clinical status related to COVID-19 on Day 14 compared with baseline on the NIAID 8-point ordinal scale. The endpoint considering the proportion of patients requiring invasive ventilation (mechanical ventilator and/or ECMO) or who are not alive, the proportion of patients in each NIAID category, and the proportion of patients alive and testing negative for COVID-19 on Day 14, Day 28, and Day 60, respectively, will be compared between the treatment groups using MH test. Overall survival, time to (first) improvement of at least 1 category on the NIAID scale and total hospitalization duration (from baseline to discharge; with death censored on last day of the observed period – at Day 28 or Day 60, respectively – depending on the analyses) will be summarized using the Kaplan-Meier method and will be compared between treatment groups using log-rank tests. Additionally, Cox proportional hazards model will be applied with treatment and the 2 stratification factors as covariables.

This document is confidential.

Page 72 of 85

Final

MetrioPharm AG MP1032	MP1032-CT05	
	Final	
MetrioPharm AG	MP1032-CT05	
MP1032	Protocol v2 0	

The odds ratio between MP1032 and SoC and placebo and SoC for the number of patients with clinical status improvement from baseline on the NIAID 8-point ordinal scale (ie, an improvement of at least 1 category) at Day 14 and Day 28 will be analyzed using a logistic regression with consideration of the 2 stratification factors.

The time to recovery of all at baseline present COVID-19 symptoms (stuffy or runny nose, sore throat, red or irritated eyes, shortness of breath, cough, low energy or tiredness, muscle or body aches, headache, chills or shivering, feeling hot or feverish, nausea, and number of times of vomit, times of diarrhea, sense of smell, sense of taste in the last 24 hours) will be presented by Kaplan-Meier estimates and figure. The change from baseline will be presented in shift tables for each single symptom, with the number and percentage of subjects in each category at post-baseline assessment time-point compared to baseline for each treatment group.

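### The endpoint of being alive and PCR-negative ignores the central Day 1 PCR result, so patients already negative before treatment count as successes in either arm and cost some precision

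*Protocol*

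**What the plan says.** - **Endpoint.** Protocol Section 6.2, other secondary endpoints: "Proportion of patients alive and testing negative for COVID-19 on Day 14, Day 28, and Day 60". No condition is set on the Day 1 result. The Bulgarian country version has the same endpoint in its Section 6.2.
- **Test.** Section 15.3: "alive and testing negative for COVID-19 on Day 14, Day 28, and Day 60, respectively, will be compared between the treatment groups using MH test".
- **Analysis set.** Section 15.2: "The ITT will serve as the basis for the analysis of efficacy". The ITT set is all randomised patients.
- **Entry test.** Section 8.1, inclusion criterion 3: "If the patient has a previous confirmation of SARS-CoV-2 (within 7 days of Day 1), the SARS-CoV-2 test at screening is not required". Section 11.5 and footnote d of Table 1 add that at screening "the local laboratory may perform COVID-19 testing by standard RT-PCR assay or equivalent test".
- **Baseline sample.** Section 11.5: "On Day 1, Day 14, Day 28, and Day 60, samples will be sent to the central laboratory for COVID-19 testing by standard RT-PCR assay". Neither eligibility nor any endpoint refers to the Day 1 result.
- **Randomisation.** Section 9.3.1 stratifies by severity and age class only.
- **Same-day screening.** Footnote a of Table 1 lets screening and Day 1 fall on one day and then waives repetition of procedures due at both visits. COVID-19 testing is marked at both.

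**The concern.** The positive test that qualifies a patient can be a week old and can come from a different assay and laboratory than the follow-up tests. Some patients may therefore be negative on the central assay before the first dose. They have nothing left to clear, yet they count as successes at Day 14, 28 and 60 if they stay alive and negative.

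Elsewhere the protocol does use the baseline. Section 15.3 defines symptom recovery on symptoms present at baseline and adjusts the NIAID change for the baseline score. This endpoint does not use its own baseline, although that baseline is collected.

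Direct antiviral activity is part of the rationale in Section 5.4, and this is the only listed endpoint that reads virus in patients. At stake is a weaker virological readout in a small proof-of-concept trial.

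**Working it through.** **The plan's own figure.** The protocol states no power for this endpoint. Its only power figure is for the primary endpoint (Section 15.1): 10% versus 30%, 76 versus 38 patients, two-sided 10%. It reproduces:
- Pooled rate = (7.6 + 11.4)/114 = 0.1667.
- SE under the null = √(0.1667 × 0.8333 × (1/76 + 1/38)) = 0.0740.
- SE under the alternative = √(0.09/76 + 0.21/38) = 0.0819.
- Power = Φ((0.20 − 1.645 × 0.0740)/0.0819) = 0.830, against the stated 83%. Also 114/0.95 = 120.

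The same method is used below.

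**Inputs for this endpoint.** From the protocol: 80 versus 40 patients and two-sided 10%. Assumed, because the protocol gives none of them:
- f = share negative on Day 1, from 5% to 30%;
- 70% (MP1032) versus 50% (placebo) alive and negative at Day 14 among Day 1 positives;
- 95% of Day 1 negatives alive and negative later, in both arms.

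**Dilution.** The rate in an arm is 0.95f + (1 − f)p, so the difference is (1 − f)(0.70 − 0.50). At f = 20%: 0.19 + 0.56 = 75% versus 0.19 + 0.40 = 59%, a difference of 16 points instead of 20.

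| f | All patients | Difference | Power, 80/40 | Power, Day 1 positives only |
|---|---|---|---|---|
| 5% | 71.25% vs 52.25% | 19 | 65.7% | 67.0% (76/38) |
| 10% | 72.5% vs 54.5% | 18 | 62.5% | 65.0% (72/36) |
| 20% | 75.0% vs 59.0% | 16 | 55.9% | 60.6% (64/32) |
| 30% | 77.5% vs 63.5% | 14 | 49.2% | 55.8% (56/28) |

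With 50% versus 30% among positives the gap is larger: 58.7% versus 63.6% at f = 10%, and 50.5% versus 59.1% at f = 20%.

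**Stratifying instead of restricting.** A simulation of the MH test (40,000 replicates, same assumptions, four equal severity-by-age strata of 20 and 10 patients) gave this power:

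| f | Four strata | Plus Day 1 PCR stratum | Day 1 positives only |
|---|---|---|---|
| 5% | 65.8% | 67.0% | 67.2% |
| 10% | 62.4% | 64.3% | 64.8% |
| 20% | 56.1% | 58.7% | 60.3% |
| 30% | 49.5% | 53.0% | 55.6% |

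If every Day 1 negative stays alive and negative, the added stratum does as well as restriction (60.1% for both at f = 20%). With equal true rates in the two arms, rejection stayed near 10% in all versions.

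The stratum restores precision, not the size of the estimate. MH weights are proportional to stratum size under 2:1 allocation, so the pooled difference at f = 20% is still 0.2 × 0 + 0.8 × 20 = 16 points. The undiluted 20 points appear only among the Day 1 positives.

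**Chance imbalance.** The SD of the between-arm difference in the Day 1 negative share is √(f(1 − f)(1/80 + 1/40)), which is 5.8 points at f = 10% and 7.7 at f = 20%. At f = 20%, one SD moves the estimate by 7.7 × (0.95 − 0.50) ≈ 3.5 points. The SE of the unadjusted difference is √(0.75 × 0.25/80 + 0.59 × 0.41/40) ≈ 9.2 points and already contains this variation.

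**The case against.** The strongest reply is that the endpoint is a status at a time point that includes survival. No objective in Section 6.1 names viral clearance. For such a status, counting every randomised patient fits the ITT basis in Section 15.2. This stands, and it is why restricting the endpoint to Day 1 positives should not replace the ITT comparison.

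A reader might infer that the planned comparison is distorted. The documents do not support that. Day 1 status is fixed before treatment, randomisation balances it in expectation, and chance imbalance is already inside the standard error.

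A reader might also infer that the protocol fixes the four severity-by-age strata for this endpoint. Section 15.3 spells them out for the primary endpoint and says only that an MH test is used here. Carrying them over is plausible but inferred, and the SAP could add a stratum. What the protocol does fix is an endpoint counted without regard to the Day 1 result, and an SAP that simply follows this text would keep the loss.

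Two further limits stand. The rates are assumed and only Day 14 is modelled. The power figures also take a PCR result for every patient, whereas Section 7.1 and footnote e of Table 1 allow telephone visits and accept missed tests.

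Finally, footnote a of Table 1 can be read as waiving a second test when screening and Day 1 coincide. Restriction to central Day 1 positives could then drop patients with a fresh local positive, for whom a stale entry test is least likely.

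**Conclusion.** The point holds as a loss of precision and a diluted risk difference on one other secondary endpoint. The dilution factor (1 − f) is exact if treatment does not alter the later status of Day 1 negatives. The size depends on f, which the documents do not give. Under 70% versus 50% among Day 1 positives, the power loss is about 1 to 2 points at f = 5 to 10% and 3 to 6 points at f = 20 to 30%. It reaches about 10 points with 50% versus 30% at the top of that range. If few patients are negative on Day 1, the matter is minor.

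There is no systematic bias, no inflation of the type I error, and no effect on the primary or key secondary results. The change is worth making because the baseline value is already scheduled for collection and costs nothing to use.

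**What to change.** Keep the endpoint in Section 6.2 and all ITT patients. In Section 15.3 and the matching synopsis text:
- Add the central Day 1 RT-PCR result (positive or negative) as a further stratum in the MH test for this endpoint.
- Where the central Day 1 result is missing, for example because screening and Day 1 coincide, use the qualifying local result. Such patients enter the positive stratum, because eligibility required a positive test.
- Report the Day 1 negative share by arm.
- Give the proportion alive and negative among central Day 1 positives as a supportive clearance analysis, which shows the undiluted difference.

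The cost is a few sentences, carried into the country versions, with no new sample or visit. The downside is more and sparser strata. If the four severity-by-age strata also apply there would be eight, and at f = 10% only 0.10 × 80 = 8 active and 0.10 × 40 = 4 placebo patients would be spread over the four negative ones. A stratum with only one arm contributes nothing. The simulation above includes this sparseness and still shows a gain at every f.

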- e. Not all assessments will be able to be performed if the Day 14, Day 28, and/or 60 visits are conducted via a telephone/virtual call (the patient's caregiver may assist during the telephone/virtual call). If the assessment can be conducted via a telephone/virtual call, the study site should record the details; otherwise, the missed assessment will not be considered a protocol deviation. If the visit is conducted by a home healthcare nurse, these assessments should be conducted, if possible; if the assessment can be conducted via home healthcare nurse, the study site should record the details; otherwise, the missed assessment will not be considered a protocol deviation. These assessments must be conducted if the visit is conducted at the study site. All efforts should be made to collect clinical laboratory assessments on Day 14 (\pm 2 days) and Day 28 (\pm 3 days). Please note: In cases in which the patient is deemed lost to follow-up, the investigator or designee must make every effort to regain contact with the patient (eg, telephone calls, letter to the patient's last known mailing address, or local equivalent methods). In cases where the patient's LAR provides informed consent on behalf of the patient, the study site should attempt to contact the LAR. Additionally, the study site should attempt to regain contact with the patient information provided by the patient/LAR at the time of informed consent. These contact attempts must be documented in the patient's medical records.
- f. Demographics will include sex, age, and race and/or ethnicity.

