p. To standardize the assessment of COVID-19 severity, respiratory rate, SpO₂, and heart rate will be measured when the patient is on room air at sea level (ie, no supplemental oxygen, if possible) and at rest for at least 5 minutes. If possible, the site should collect the information from each patient at the same time each day (±1 hour).

q. Record the patient's clinical status related to COVID-19 on the NIAID 8-point ordinal scale and also record the date and time for each individual component of the NIAID 8-point ordinal scale including: invasive or non-invasive mechanical ventilation/ECMO start/stop, high-flow/mask oxygen start/stop, supplemental oxygen start/stop (nasal cannula, liter flow [and its conversion to FiO₂], other delivery services), hospital discharge (whether with limitations or without limitations), hospitalization type (eg, transfer to ICU) start/stop, and (if applicable) death, cause of death (including relatedness to COVID-19), and date/time of death. If possible, the site should collect the information from each patient at the same time each day (±1 hour).

r. The EQ-5D-5L (Appendix 2) is only required for discharged patients and at the following visits: day of discharge, Day 60, and Early Termination visit (if applicable). The EQ-5D-5L is not required for patients who remain hospitalized until study end.

- s. The limited physical examination and clinical laboratory assessments on Day 8 (\pm 3 days) will be collected in all patients who remain hospitalized. If the patient is discharged before Day 8 (\pm 3 days), the site should arrange to have the physician assess the patient via a telephone/virtual call. If the physician determines during the telephone/virtual call that the limited physical examination and clinical laboratory assessments are clinically indicated, then the site should arrange for an outpatient visit to collect these assessments.

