- 5. Hospitalized, not requiring supplemental oxygen but requiring ongoing medical care (COVID-19 related or otherwise)
- 6. Hospitalized, not requiring supplemental oxygen and no longer requires ongoing medical care (used if hospitalization was extended for infection-control reasons)
- 7. Not hospitalized, limitation on activities, and/or requiring home oxygen
- 8. Not hospitalized, no limitations on activities

Please note: Patients requiring oxygen before COVID-19 and returning to baseline oxygen use will be considered improved (ie, not requiring supplemental oxygen). Patients with a limitation on activities before COVID-19 and returning to baseline activity will be considered improved.

At the visits specified in the Schedule of Assessments (Table 1), record the date and time for each individual component of the NIAID 8-point ordinal scale including: invasive or noninvasive mechanical ventilation/ECMO start/stop, high-flow/mask oxygen start/stop, supplemental oxygen start/stop (nasal cannula, liter flow [and its conversion to FiO₂], other delivery services), hospital discharge (whether with limitations or without limitations), hospitalization type (eg, transfer to ICU) start/stop, and (if applicable) death, cause of death (including relatedness to COVID-19), and date/time of death. If possible, the site should collect the information from each patient at the same time each day $(\pm 1 \text{ hour})$.

A standard conversion for liter flow oxygen to FiO₂ is presented in Table 4.

	FiO2 (%)
Room air	21
1 L/min	24
2 L/min	27
3 L/min	30
4 L/min	33
5 L/min	36
6 L/min	39

Table 4 **Standard Conversion for Liter Flow Oxygen**

If there is use of a venturi mask (air-entrainment mask), the FiO_2 is based on the nozzle use and should also be recorded.

This document is confidential.

Page 57 of 85

14 Health-related Quality of Life Assessment

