12.2 Vital Signs

Vital signs (systolic and diastolic blood pressure, heart rate, respiration rate, SpO₂, and body temperature) will be evaluated at the visits indicated in the Schedule of Assessments (Table 1). All vital signs will be measured after the patient has been resting for at least 5 minutes. Blood pressure measurements are to be taken in the same arm for the duration of the study. Moreover, additional vital signs may be performed as needed in case of any cardiac AE.

Additionally, body weight (without shoes) will be recorded at screening, Day 1, Day 14, Day 28, Day 60, and day of discharge (applicable); height (without shoes) will be recorded at screening only. Body mass index will be calculated whenever weight is recorded.

Vital sign measurements will be repeated if clinically significant or machine/equipment errors occur. Out-of-range blood pressure, respiratory rate, heart rate measurements, or SpO₂ will be

This document is confidential.

Page 59 of 85

MetrioPharm AG	MP1032-CT05	
MP1032	Final	
MetrioPharm AG	MP1032-CT05	
MP1032	Protocol v2.0	

repeated at the investigator's discretion. Any confirmed, clinically significant vital sign measurements must be recorded as AEs.

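### The exploratory SpO2/FiO2 endpoint is limited to survivors, and the listed recording items name no FiO2 for high-flow oxygen, non-Venturi masks or ventilation, so the arms may be compared in outcome-selected subsets

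*Protocol*

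**What the plan says.** Section 6.2 lists, among the exploratory endpoints, the change in the SpO2/FiO2 "ratio (for patients alive) on Day 14 or Day 28 compared with baseline". No value is assigned to patients who have died.

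The two components come from different places.

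- **SpO2** is a vital sign (section 12.2: "Vital signs (systolic and diastolic blood pressure, heart rate, respiration rate, SpO₂, and body temperature"). Table 1, footnote e, concedes that "Not all assessments will be able to be performed if the Day 14, Day 28, and/or 60 visits are conducted via a telephone/virtual call", and an assessment missed for that reason is not a deviation.
- **FiO2** is covered by section 11.3 and Table 1, footnote q. For ventilatory support and high-flow or mask oxygen the listed items are "mechanical ventilation/ECMO start/stop, high-flow/mask oxygen start/stop". FiO2 is named only within the supplemental-oxygen item, as "liter flow [and its conversion to FiO₂". Section 11.3 adds: "A standard conversion for liter flow oxygen to FiO₂ is presented in Table 4". That table runs from room air (21%) to 6 L/min (39%). There is one further provision: "If there is use of a venturi mask (air-entrainment mask), the FiO_2 is based on the nozzle use and" should also be recorded.

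Elsewhere death does receive a value. Section 6.2 scores it as 1 on the NIAID scale, and section 15.3 gives it the maximum duration for ICU, ventilation and ECMO days.

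**The concern.** A ratio needs both components on the day. On the listed items, a living patient on high-flow oxygen, non-invasive ventilation, invasive ventilation or ECMO has no FiO2, and a patient who has died is outside the definition. Exclusion criterion 2 keeps out critical COVID-19, which includes ventilation and high-flow oxygen as defined there. Patients found at NIAID 2 or 3 on Day 14 have therefore, almost without exception, deteriorated since Day 1. They are the patients in whom an oxygenation measure should move most.

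Whether a patient is scored thus depends on the outcome that the drug is meant to change. The comparison is then between two subsets selected after randomization, and it loses the protection that randomization gives. The analysis plan can define how missing values are handled, but it cannot recover an FiO2 that was never written down.

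**Working it through.** **1. The plan's own figure.** The protocol gives no figure for this endpoint. The only plan figures borrowed below are the Day 14 progression totals in section 15.1 (10% on MP1032, 30% on placebo). The calculation they support reproduces:

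- pooled proportion = (38 × 0.30 + 76 × 0.10)/114 = 0.1667
- null SE = √(0.1667 × 0.8333 × (1/38 + 1/76)) = 0.0740
- alternative SE = √(0.21/38 + 0.09/76) = 0.0819
- power = Φ((0.20 − 1.645 × 0.0740)/0.0819) = Φ(0.955) = 0.83, and 114/0.95 = 120

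This concerns the primary endpoint and says nothing about SpO2/FiO2.

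**2. Who can be scored from the listed items.**

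| Status on the day | FiO2 among the listed items |
|---|---|
| 1, dead | excluded by definition |
| 2, invasive ventilation or ECMO | none; start/stop only |
| 3, non-invasive ventilation or high flow | none; start/stop only |
| 4, flow up to 6 L/min | yes, Table 4 |
| 4, Venturi mask | yes, from the nozzle |
| 4, other mask or flow above 6 L/min | none; no conversion |
| 5–8, room air | 21% in Table 4, but SpO2 may be missing after a telephone visit |

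**3. What selection could do.** All state mixes and ratios here are assumptions. Assumed ratios: room air 97/0.21 = 462; low flow 94/0.30 = 313; high flow or non-invasive ventilation 93/0.55 = 169; invasive ventilation 93/0.70 = 133. Death is set to 0 where it is included. Day 14 mixes, in % dead / invasive / high flow / low flow / room air:

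| Mix | Placebo | MP1032 |
|---|---|---|
| A, all bad states cut by two thirds | 6/4/6/14/70 | 2/1.33/2/4.67/90 |
| B, benefit at the severe end | 10/6/9/5/70 | 2/1/2/5/90 |
| C, severe states moved to low flow | 6/6/10/8/70 | 3/2/3/22/70 |
| D, effect on low flow only | 3/2/3/22/70 | 3/2/3/2/90 |
| E, worse at severe end, better at low flow | 4/3/5/18/70 | 8/5/7/4/76 |

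Mixes A, B and D keep the protocol's 30% versus 10%. C has 30% in both arms, and E has 30% versus 8 + 5 + 7 + 4 = 24%.

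The arm mean is Σ(share × ratio)/Σ(share) over the states kept. For A as scorable:

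- placebo (0.14 × 313.3 + 0.70 × 461.9)/0.84 = 437
- MP1032 (0.0467 × 313.3 + 0.90 × 461.9)/0.9467 = 455
- difference 17.4 before rounding

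MP1032 minus placebo:

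| Mix | All patients, death = 0 | Alive, FiO2 for all | Alive, FiO2 only on low flow or room air |
|---|---|---|---|
| A | 52.8 | 37.3 | 17.4 |
| B | 73.9 | 42.6 | 2.1 |
| C | 26.7 | 15.3 | −20.3 |
| D | 29.7 | 30.6 | 32.3 |
| E | −10.1 | 6.8 | 23.0 |

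In A the patients without a ratio are 6 + 4 + 6 = 16% of placebo (0.16 × 40 = 6.4 patients) and 2 + 1.33 + 2 = 5.33% of MP1032 (0.0533 × 80 = 4.3 patients).

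**4. Telephone visits.** Suppose 60% of room-air patients in A also lack SpO2. The scored share becomes 0.14 + 0.4 × 0.70 = 42% on placebo and 0.0467 + 0.4 × 0.90 = 41% on MP1032, and the last-column difference rises from 17.4 to 32.5.

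These are differences in Day 14 level. The endpoint is change from baseline, and baseline values in the selected subsets would add a further unknown.

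**The case against.** The limit to survivors is an explicit definition, and an oxygenation ratio has no natural value after death. The severe end is captured elsewhere: in the primary endpoint, Day 28 mortality, the NIAID change with death scored 1, and the endpoint of invasive ventilation or death. The recording list is introduced as inclusive, so it is open, and the eCRF, which is not shown, may already hold an FiO2 field. Section 15.3 names no test for this endpoint and confines the further 10% comparisons to secondary endpoints, although the synopsis is looser. A worst-rank composite would partly duplicate the NIAID analysis.

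Most of this stands, and it limits the point to one exploratory measure. It does not remove the gap: the protocol is what tells sites what to record, and for these devices it names start and stop alone.

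Four stronger readings are tempting and are not supported:

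- A reader might infer that any real difference must shrink. Mixes C, D and E show otherwise.
- A reader might infer that no mask patient has an FiO2. Section 11.3 provides for the Venturi mask.
- A reader might infer that mainly patients who did well are scored. Telephone visits remove discharged patients as well. Section 7.1 prefers on-site Day 14 and Day 28 visits, and the Bulgarian version requires them, so the extent is unknown.
- A reader might want to state a loss of power. With no test named and every split assumed, there is no basis for one.

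**Conclusion.** The point holds as a minor one. The endpoint excludes the dead, and the listed items name no FiO2 for high-flow oxygen, non-Venturi masks, non-invasive or invasive ventilation, or ECMO. If only those items are recorded, living patients at NIAID 2 or 3 cannot be scored, and the arms are compared in subsets selected by outcome.

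The direction of the bias is uncertain. Shrinkage is likely if the drug helps across all bad states, but a reversed sign or harm shown as benefit is possible. Every size given is illustrative, because only the 10% and 30% totals come from the protocol. The gap also depends on the unseen eCRF following the protocol list and nothing more.

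It would be wrong to conclude that the trial would hide harm. At most this one measure could mislead; the primary and key secondary conclusions do not depend on it.

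**What to change.** - In section 11.3 and Table 1, footnote q, add the set or delivered FiO2 for every oxygen or ventilation device (NIAID scores 2 to 4) at Day 1, Day 14 and Day 28.
- Keep the summary in survivors, and report beside it, per arm, the number dead and the number alive but unscored.
- Add a supplementary rank-based comparison with deaths ranked worst, in line with the treatment of death for ICU, ventilation and ECMO days in section 15.3.
- Make the same edits in the country versions; the Bulgarian version repeats the endpoint definition in its section 6.2.

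The cost is one more recorded field per device and one extra exploratory analysis. If the eCRF already holds the field, only the text changes. The supplementary result is a rank comparison and cannot be read as a mean change in the ratio, which is why it belongs beside the survivor summary and does not replace it.
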